## **A5.** PRIMETIME Information Giving Study (IGS) Protocol

### **BACKGROUND**

## Patient uncertainty regarding de-escalation of treatment studies

PRIMETIME is investigating whether we can identify a highly selected group of women with a very low risk of the breast cancer returning, for whom the side effects of radiotherapy may outweigh the benefits and adjuvant breast radiotherapy can be safely avoided. Research studies are conducted when there is uncertainty regarding the optimal treatment option. Furthermore patients may experience uncertainty regarding whether to participate in a clinical trial. This uncertainty may be compounded in a de-escalation of treatment study where a component of standard treatment is omitted. The state of uncertainty regarding which course of action to take in health-care-related decisions is known as decisional conflict [1]. Defining characteristics of decisional conflict include voicing uncertainty, hesitation between choices, delayed decision making and questioning personal values (personal importance of outcomes) and beliefs when attempting decision making [1]. A number of factors are thought to contribute to decisional conflict which include lack of information regarding alternative treatments and consequences, unclear patient values and the lack of skills to make or implement decisions [1]. Reducing patient uncertainty may facilitate the decision making process for patients.

# Use of decision aids to manage patient uncertainty

One way of optimising decision making for patients who face uncertainty is to use decision aids. Decision aids may help patients understand the benefits and risks of treatment options, consider the value they place on benefits and risks and participate actively with their clinicians in deciding treatment options. A Cochrane review of decision aids for people facing health treatment or screening decisions [2] found high quality evidence that decision aids improved patient knowledge regarding treatment options (using study specific questionnaires) and reduced their decisional conflict. There is also evidence that decision aids encourage patients to take a more active role in decision making and improve accurate perceptions of risk. A meta-analysis of cancer related decision aids for patients entering randomised controlled trials demonstrated that patients receiving decision aids had reduced decisional conflict [3].

The IBIS II trial investigated the use of a decision aid in a randomised controlled trial of an aromatase inhibitor in two patient groups; patients at high risk of breast cancer (prevention

group) and patients with Ductal Carcinoma In Situ (DCIS) (treatment group). The authors found there was no difference in their primary outcome of decisional conflict however patients who received the decision aid in the 'treatment' group had higher knowledge post decision compared with patients who did not receive the decision aid. In the 'prevention' group patients who received the decision aid had lower decisional regret at follow-up compared with those who did not receive the decision aid [4]. A study involving women aged 70 or above with stage 1 breast cancer considering radiotherapy after lumpectomy found after using a decision aid that patients had a statistically significant reduction in decisional conflict, increased clarity of the benefits and risks and improved general treatment knowledge [5]. Both studies described are both small single centre studies.

It is not known whether the introduction of a decision aid video in addition to written patient information will reduce decisional conflict within the context of the PRIMETIME study where the risks and benefits of radiotherapy are being discussed and the concept of treatment de-escalation is being introduced. This requires assessment within the context of a prospective research study.

### Design of the PRIMETIME Information Giving Study

We propose to introduce a decision aid (in video format) in addition to written patient information, in order to optimise the decision making process for patients who are considering participating in PRIMETIME. The study will investigate the effect of the decision aid on patients' decisional conflict regarding their decision of whether or not to participate in the PRIMETIME main study.

We plan to use a 'study within a trial' approach or 'SWAT' as this can assess different ways of designing, conducting, analysing and evaluating studies through the conduct of research within research [6]. A cluster stepped-wedge trial design will be used for the PRIMETIME Information Giving Study. A cluster stepped-wedge trial consists of the sequential implementation of an intervention (the decision aid video) to participants (or in the case hospital sites) grouped within clusters over a number of time periods [7]. An example of a cluster is a group of hospitals under one National Health Service trust. All clusters will receive the intervention by the end of the study however the order in which clusters initiate the intervention is determined at random [7]. In general, cluster stepped-wedge trials are designed to study the effects of a new intervention implemented at cluster level, but which is experienced and measured at the individual patient level [8]. The justification for

implementing the decision aid video at cluster level is to ensure all patients being treated at

a study centre will receive the same information (either written patient information or

written patient information in conjunction with video) over pre-specified time periods. If the

decision aid was implemented at individual patient level then patients in a centre may

discuss the different formats of information they are receiving. This may compromise the

interpretation of decisional conflict.

We hypothesise that the decision aid video in addition to written patient information will

reduce decisional conflict and the stepped-wedge trial design ensures that by the end of the

PRIMETIME Information Giving Study all clusters will have used the decision aid.

Furthermore, in a cluster stepped-wedge trial each cluster acts as its own control, increasing

the statistical power of the study.

If the PRIMETIME Information Giving Study demonstrates that the introduction of a decision

aid can reduce decisional conflict regarding entry into the PRIMETIME main study, this may

provide evidence to support increasing resources into the development of decision aids for

de-escalation of treatment studies.

**STUDY POPULATION** 

Patients who are approached for the PRIMETIME main study will be eligible for the

PRIMETIME Information Giving Study.

**STUDY OBJECTIVES** 

Primary objective;

• To assess whether the introduction of a decision aid video in addition to written

patient information reduces patients' decisional conflict.

Secondary objectives;

Acceptance of entry into the PRIMETIME main study ie. the proportion of

participants who consented to the PRIMETIME main study of all patients who were

eligible for and given information about the PRIMETIME main study.

• Acceptance of recommended treatment in the PRIMETIME main study ie. the

proportion of patients who accepted their recommended treatment of all patients

who consented to the PRIMETIME main study

**STUDY DESIGN** 

All centres open to recruitment for PRIMETIME will be included in the PRIMETIME

Information Giving Study. The PRIMETIME Information Giving study will open in each centre

when the first patient in that centre consents to the PRIMETIME Information Giving Study.

In addition to the written PRIMETIME main study patient information sheet that patients

already receive, phased implementation of the decision aid video will take place using a

cluster randomised stepped-wedge approach. A cluster consists of the radiotherapy centre

and any peripheral centres referring into the radiotherapy centre. Each cluster will receive

the PRIMETIME main study patient information sheet and be randomised to receiving the

decision aid video at 2, 4, or 6 months after the first patient within the cluster consents to

the PRIMETIME Information Giving Study.

Allocation to which time point the cluster will start using the decision aid will be by

minimisation (balanced on level of recruitment per centre in previous breast radiotherapy

trials) and be performed by the ICR-CTSU. Based on experience with ICR-CTSU trials, clusters

included in the PRIMETIME Information Giving Study will be categorised into 'high' versus

'low' recruiters according to average number of patients recruited per month in previous

ICR-CTSU trials (eg. the IMPORT HIGH and FAST FORWARD). Recruitment to previous breast

[figure not shown]
radiotherapy trials has been chosen to ensure that higher recruiting centres do not all

receive the decision aid at the same time point. The justification for delaying when the

intervention will commence is to ensure that there are sufficient participant numbers for the

assessment of decisional conflict prior to and after introduction of the decision aid video.

Figure 1: Proposed implementation of PRIMETIME Information Giving Study using a Cluster Stepped-Wedge Trial design

All clusters will begin the study in Group A and switch over to Group B at either 2, 4 or 6 months from when the first patient per cluster enters the PRIMETIME Information Giving Study. Group A will be given Version A of the PRIMETIME main study patient information sheet. Group B will be given Version B of the PRIMETIME main study patient information sheet. The description of the PRIMETIME Information Giving Study will differ between Version A and B with Version B specifying that patients will be provided with a video. This will be the only difference between Version A and B of the PRIMETIME main study patient information sheet.

Please Note – sites should not make patients aware of the availability of the video before the switch over date.

Group A

In Group A clusters, participants will have a discussion with a healthcare professional and be

provided with Version A of the PRIMETIME main study patient information sheet. After the

patient has made their decision regarding entry into PRIMETIME, they will be presented with

Questionnaire A which includes baseline demographics, questions regarding the information

provided and the decisional conflict questionnaire [1]. Return of the Questionnaire indicates

consent to the PRIMETIME Information Giving Study.

Group B

In Group B clusters, participants will have a discussion with a healthcare professional and be

provided with Version B of the PRIMETIME main study patient information sheet and given

access to the decision aid video. The video must be viewed after the consultation with the

healthcare professional and after the patient has read the PRIMETIME main study patient

information sheet. The video must also be viewed prior to the patient making their decision

regarding entry into the PRIMETIME main study. After the patient has made their decision

regarding entry into PRIMETIME, they will be presented with Questionnaire B which includes

baseline demographics, questions regarding the information provided and the decisional

conflict questionnaire [1]. Return of the Questionnaire indicates consent to the PRIMETIME

Information Giving Study.

**ENDPOINTS** 

**Primary Endpoint** 

The primary endpoint for this study is decisional conflict as measured on the decisional

conflict scale [1].

Secondary Endpoints;

Acceptance of entry into the PRIMETIME main study ie. the proportion of

participants who consented to the PRIMETIME main study of all patients who were

eligible for and given information about the PRIMETIME main study.

Acceptance of recommended treatment in the PRIMETIME main study ie. the

proportion of patients who accepted their recommended treatment of all patients

who consented to the PRIMETIME main study.

**FOLLOW-UP** 

There is no additional follow-up required for the PRIMETIME Information Giving Study.

# **STATISTICAL CONSIDERATIONS**

Statistical design and sample size justification

The target sample size for the PRIMETIME Information Giving Study is 264 patients. This sample size is based on three steps in the cluster stepped-wedge trial design (at 2, 4 and 6 months) of 33 clusters (11 per step), with 2 patients per cluster per 2 month period. There is limited literature on what is a clinically significant reduction in decisional conflict. Two small single centre studies conducted in similar populations to patients in PRIMETIME found effect sizes around 0.40, with standard deviations for the total Decisional Conflict Scale score ranging from 11-25 [4,5]. As this is a cluster randomised trial, the sample size estimation needs to allow for possible clustering effects. However there is no data available on likely values of the intraclass correlation (ICC) for the Decisional Conflict Scale, and so estimates have been calculated across the range of ICC values from 0 to 1. Assuming an alpha of 0.05, 264 patients from 33 clusters would have at least 80% power for all values of the ICC to detect a 10-point difference in total score for the Decisional Conflict Scale (effect size=0.55, assuming standard deviation=18). If this target is not achievable, then 240 patients from 30 centres would provide at least 80% power to detect an effect size of 0.55 across most of the range of ICC values. The figure below illustrates the power for different scenarios according to value of ICC and number of clusters (with total number of patients also shown).

[figure not shown]

Figure 2: Power when intraclass correlation is varied

### Treatment allocation

Each cluster will receive the PRIMETIME main study patient information sheet. Each cluster will be allocated to receive the PRIMETIME main study patient information sheet and

decision aid video at 2, 4 or 6 months from when the first patient consents to the

PRIMETIME Information Giving Study. All centres within a cluster will be allocated to

receiving the decision aid at the same time point. Clusters will be allocated using

minimisation performed by the ICR-CTSU. Each cluster will be allocated a status of high

versus low recruiter based on their recruitment into previous ICR-CTSU trials (eg.IMPORT

HIGH and FAST FORWARD), and recruitment stratum used as a balancing factor in the

minimisation.

**STATISTICAL ANALYSIS PLAN** 

The data will be analysed on the intention to treat (ITT) analysis set. According to the

intention to treat principle, clusters will be analysed according to randomised decision aid

video start time regardless of when the cluster started using the decision aid video [9].

Primary endpoint

Only patients who return questionnaires (i.e. consent to the PRIMETIME Information Giving

Study) will be analysed, regardless of whether they consent to participate in the PRIMETIME

main study.

The mean decisional conflict score pre- and post-implementation of the decision aid video

will be calculated (with 95% confidence interval). Calendar time is a possible confounder and

therefore any effect seen could be (partly or in full) due to underlying temporal trend [9]. To

adjust for calendar time and clustering the methods detailed in Hussey and Hughes [10] will

be followed, where a linear mixed model will be fitted with a random effect for cluster and a

fixed effect for each step.

A sensitivity analysis will be performed to compare the decisional conflict of those who

stated they watched the decision aid video (in Questionnaire B) compared to those who

stated they did not watch the decision aid video (in Questionnaire B) and those who were

not in a cluster using the decision aid video (i.e. were given Questionnaire A to complete).

Secondary endpoints

Acceptance of PRIMETIME main study entry - all participants who were given information

and were eligible to enter the PRIMETIME main study will be analysed. This follows an ITT

analysis where patients will be analysed according to the information (PRIMETIME main

study information sheet versus PRIMETIME main study information sheet and decision aid

video) their cluster was assigned to at that step. Therefore patients will be included

regardless of whether they returned a questionnaire.

A sensitivity analysis will be performed to compare the acceptance of PRIMETIME main

study entry in patients who stated they watched the decision aid video (in Questionnaire B)

compared to those who stated they did not watch the decision aid video (in Questionnaire

B) in addition to those who were not in a cluster using the decision aid video (i.e. were given

Questionnaire A to complete).

Acceptance of recommended treatment in patients consenting to the PRIMETIME main study

- all participants who were recruited into the main PRIMETIME main study will be analysed.

This follows an ITT analysis where patients will be analysed according to the information

(PRIMETIME main study information sheet versus PRIMETIME main study information sheet

and decision aid video) their cluster was assigned to at that step. Therefore patients will be

included regardless of whether they returned a questionnaire.

A sensitivity analysis will be performed to compare the acceptance of recommended

treatment in patients consenting to the PRIMETIME main study in patients who stated they

watched the decision aid video (in Questionnaire B) compared to those who stated they did

not watch the decision aid video (in Questionnaire B) in addition to those who were not in a

cluster using the decision aid video (i.e. were given Questionnaire A to complete).

Both secondary endpoints will be analysed using a logistic regression model with a cluster

level fixed effect for assigned group at that step (PRIMETIME main study information sheet

versus PRIMETIME main study information sheet and decision aid video), with a random

effect for cluster and a fixed effect for each step [9, 10].

An interim analysis to review emerging data is planned in the first quarter of 2019 and will

include the facility to include data in a confidential PhD thesis. The final analysis will take

place once all the clusters have received the decision aid.

Data acquisition – Questionnaires will be completed at each centre by the patient and then posted back to the ICR-CTSU for data entry onto the PRIMETIME Information Giving Study database.

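### Information Giving Study: the models are said to adjust for calendar time, but their step term counts time since each cluster opened

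*Protocol*

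**What the plan says.** All of this is in Appendix A5 of the protocol.

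- **Aim.** The Statistical Analysis Plan states: "Calendar time is a possible confounder and" an apparent effect may reflect an underlying trend. It then says that to "adjust for calendar time and clustering the methods detailed in Hussey and Hughes [10] will" be followed.
- **Primary model.** A linear mixed model with a random effect for cluster and a "fixed effect for each step". No calendar date or calendar period enters.
- **Secondary models.** The logistic models for both acceptance endpoints use the same structure, with a random "effect for cluster and a fixed effect for each step [9, 10".
- **What a step is.** The sample size text describes "three steps in the cluster stepped-wedge trial design (at 2, 4 and 6 months) of 33 clusters (11 per step".
- **Where the clock starts.** Study Design has each cluster randomised to the "decision aid video at 2, 4, or 6 months after the first patient within the cluster consents to" the sub-study, and says that clusters "switch over to Group B at either 2, 4 or 6 months from when the first patient per cluster enters". The sub-study opens in a centre "when the first patient in that centre consents to the PRIMETIME Information Giving Study".
- **Allocation.** Switch time is set by minimisation on past recruitment level (high or low). Opening date is not a balancing factor.

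**The concern.** A fixed effect for step adjusts for calendar time when all clusters start together, because each step is then a calendar period. Here each cluster has its own start. A woman seen in months 2 to 4 of a cluster that opened at the beginning of the study, and one seen in months 2 to 4 of a cluster that opened a year later, receive the same step effect although they were seen a year apart. The appendix therefore claims an adjustment that its models do not make.

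At stake is how far a change in calendar time, such as new external evidence or altered counselling, can move the estimated effect of the video on decisional conflict. The main trial's endpoints are not involved.

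**Working it through.** **1. The plan's own figure.** Inputs from Statistical Considerations: I = 33 clusters, 11 per switch time; T = 4 two-month periods; m = 2 women per cluster-period; SD 18; difference 10; alpha 0.05 (two-sided assumed).

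N = 33 × 4 × 2 = 264, as stated.

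The Hussey–Hughes variance of the treatment effect is

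Var = I·s²·(s² + T·t²) / [(I·U − W)·s² + (U² + I·T·U − T·W − I·V)·t²],

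with s² = 324(1 − ICC)/2 and t² = 324·ICC.

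- U = 11 × (3 + 2 + 1) = 66
- W = 11² + 22² + 33² = 1694
- V = 11 × (9 + 4 + 1) = 154
- I·U − W = 2178 − 1694 = 484
- U² + I·T·U − T·W − I·V = 4356 + 8712 − 6776 − 5082 = 1210

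Results:

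- ICC 0: Var = 33 × 162/484 = 11.05, SE 3.32, power = Φ(10/3.32 − 1.96) = 85.3%.
- ICC 0.12 (about the minimum): s² = 142.56, t² = 38.88, Var = 12.08, SE 3.48, power 82.0%.

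The claim of at least 80% power at every ICC is reproduced.

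**2. What the step effect does and does not absorb.** For any woman, calendar date = opening date of her cluster + time since opening. Under a linear calendar trend, the step effect absorbs the second part. The random cluster effect takes up the first, fully as the ICC approaches 1 and in part otherwise. What is left is non-linear trend, together with whatever difference in opening dates chance has produced between early-switching and late-switching clusters.

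The step term does most of the necessary work. In simulation with a null effect, a linear trend of 1 point per month and ICC 0.1, omitting any time term gave a bias of about −3.5 to −3.8 points. With the step term, the mean estimate stayed within about 0.15 point of zero for every trend tried.

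**3. Size of what remains (linear model).** The documents give neither a calendar trend nor a spread of opening dates, so both are assumptions. Layout as in step 1, ICC 0.05, one 10-point calendar shift, openings spread over 6 to 24 months, 1500 random allocations per row. Sampling noise is removed, so the SD is the trend's own contribution to a single estimate.

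| Openings over | SD, step only | SD, step + calendar quarter |
|---|---|---|
| 6 months | 1.24 | 0.75 |
| 12 months | 1.22 | 0.49 |
| 18 months | 1.26 | 0.41 |
| 24 months | 1.22 | 0.36 |

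Repeat runs gave step-only SDs of 1.2 to 1.3, a 95th percentile of the absolute error of about 2.4 to 2.6, and mean error about zero. Placing the drop differently and varying the ICC from 0.02 to 0.5 gave SDs of about 0.7 to 1.4. An 18-point shift (one full SD of the scale) gave SDs of 2.2 to 2.3.

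**4. In proportion.** The model SE at ICC 0.05 is 3.44. Adding an independent error of SD 1.25 gives √(3.44² + 1.25²) = 3.66, about 6% more.

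**5. Cost of adding calendar quarter.** With no calendar trend, the SE goes from 3.44 to between 3.47 and 3.55: 3.47/3.44 = 1.01 and 3.55/3.44 = 1.03.

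**The case against.** **The text may mean calendar steps.** The model sentence does not define step again, Figure 1 is not shown, and the treatment allocation paragraph does not repeat that the months are counted per cluster. The coding of time is also often left to an analysis plan. This has some force. But Study Design states the per-cluster clock twice, the sample size text ties the steps to 2, 4 and 6 months, and the secondary analyses speak of what a cluster was assigned to at a step. The protocol fixes the model and states what it achieves, so this is a wrong statement and not a detail left open. If calendar steps were intended, the wording still needs correcting.

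**A reader might infer that calendar trend biases the result.** The documents do not support that. Switch times are randomised, so opening dates are balanced in expectation and the mean error is about zero. Full alignment of opening date with switch time would give an error of about 3.8 points for a 10-point drop. Minimisation on recruitment level does not rule that out, but it is an extreme case, not an expected one.

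**A reader might infer invalid standard errors or inflated type I error.** That does not stand either. A fitted mixed model takes much of the remaining trend into its estimated variances. In 3000 runs per scenario (ICC 0.05, openings over 12 months), type I error was 5.8% with no trend, 6.0% with a 10-point shift and 6.0% with an 18-point shift. Clearly higher values came only from combinations such as a full-SD shift with every cluster opening within six months (9.1%), for which the protocol gives no basis.

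**The assumed shifts are large.** This stands: 10 points is the whole target difference. The figures show what could happen, not what is expected.

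**Conclusion.** The stated adjustment and the specified models do not match. With clusters opening on different dates, the step effect adjusts for time since opening, in the primary model and in both logistic models. The consequence is modest: extra random error from chance imbalance of opening dates, with SD about 1.2 to 1.3 points and 95th percentile about 2.5 under an assumed 10-point calendar shift at ICC 0.05, against a 10-point target. It is not systematic bias, and no claim of inflated type I error follows. The stated power and sample size stand. The size rests on assumed trends and opening spreads and was calculated for the linear model only; nothing was calculated for the logistic models. This is a minor point that is cheap to put right.

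**What to change.** Keep the random cluster effect and the step effect, and add a fixed effect for calendar period to the linear mixed model, for example the calendar quarter. Take it from whichever patient-level date is used to assign each woman to a step, and name that date. Add calendar period to the two logistic models as well, with coarser periods if events are sparse.

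Add the calendar term; do not substitute it for the step term. When two-month calendar periods replaced the steps and openings fell within six months, a 10-point drop left a mean error of about −0.4 to −0.5 point at ICC 0.02 to 0.1.

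At minimum, reword the Statistical Analysis Plan in Appendix A5 to say that the step effect adjusts for time since the cluster opened.

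The cost is a change of wording and one covariate. If there is no calendar trend, the linear-model standard error rises by about 1 to 3%; the cost in the logistic models was not calculated.

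### The Information Giving Study minimises clusters on recruitment stratum but leaves that stratum out of the listed models; adding it is a minor improvement at almost no cost

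*Protocol*

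**What the plan says.** All references are to Protocol Appendix A5, the sub-study's own protocol.

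- **Allocation.** Under Study Design and Treatment allocation, each cluster is classed as a high or low recruiter from its record in previous trials and is allocated to start the video at 2, 4 or 6 months. Allocation is by minimisation, "and recruitment stratum used as a balancing factor in the" minimisation. The reason given under Study Design is to keep the higher-recruiting centres from all switching at the same time.
- **Primary model.** Under Statistical Analysis Plan, "a linear mixed model will be fitted with a random effect for cluster and a" fixed effect for each step, following the cited stepped-wedge method.
- **Secondary models.** Acceptance of main-study entry and acceptance of recommended treatment are each analysed by logistic regression on assigned group, with a random "effect for cluster and a fixed effect for each step [9, 10"].
- **Power.** The design is "of 33 clusters (11 per step), with 2 patients per cluster per 2 month period". With 264 patients it "would have at least 80% power for all values of the ICC to detect a 10-point difference" ("effect size=0.55, assuming standard deviation=18"). The protocol adds that "there is no data available on likely values of the intraclass correlation (ICC) for the Decisional Conflict Scale".

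Recruitment stratum appears in the allocation text but in none of the three model descriptions.

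**The concern.** An analysis normally conditions on the factors used to balance the allocation. If such a factor is related to the outcome and is left out, the reported standard error still contains variation that the allocation has already balanced, so it is wider than it needs to be. Any imbalance that remains also goes unadjusted.

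The random cluster effect does not settle the matter. Fixed cluster effects would remove a factor that is constant within a cluster. A random effect only counts that factor as part of the between-cluster variance. The omission therefore matters to the extent that the design uses between-cluster comparisons and the stratum explains between-cluster variance. What is at stake is a small amount of precision on the primary endpoint and agreement between allocation and analysis on all three endpoints.

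**Working it through.** **Inputs from Appendix A5, Statistical Considerations.** I = 33 clusters (11 per sequence), T = 4 two-month periods, m = 2 patients per cluster-period (33 × 4 × 2 = 264), SD 18 (total variance 324), difference 10, alpha 0.05.

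**Assumptions.** The test is two-sided (the document does not say). The ICC is varied, because the protocol has no value. R², the share of between-cluster variance explained by the stratum, is varied from 0 to 0.50, because the documents give none. The stratum is taken as balanced over the three sequences.

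**Formula (Hussey and Hughes).** With τ² = ICC × 324 and s² = (1 − ICC) × 324/2,

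Var = I s²(s² + Tτ²) / [(IU − W)s² + (U² + ITU − TW − IV)τ²].

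- U, the number of exposed cluster-periods: 11 × (3 + 2 + 1) = 66
- W, the sum of squared period totals: 0 + 11² + 22² + 33² = 1694
- V, the sum of squared cluster totals: 11 × (9 + 4 + 1) = 154
- IU − W = 2178 − 1694 = 484
- U² + ITU − TW − IV = 4356 + 8712 − 6776 − 5082 = 1210

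**Step 1: reproduce the stated power, without the stratum.** At ICC 0.10, τ² = 32.4 and s² = 145.8. Var = 33 × 145.8 × 275.4 / (484 × 145.8 + 1210 × 32.4) = 1,325,060 / 109,771 = 12.07, so SE = 3.474. Power = Φ(10/3.474 − 1.96) = 82.1%. Over the ICC range, power is 85.3% at ICC 0, has its minimum of 82.0% near 0.12, and then rises towards 100%. With a difference of 0.55 × 18 = 9.9 the minimum is 81.3%. The claim of at least 80% for every ICC is reproduced. For the fallback of 30 clusters (240 patients) the minimum is 78.3%, and power is at least 80% over about 81% of the ICC range, which agrees with the protocol's claim for most of the range.

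**Step 2: how much information is between clusters.** A purely within-cluster analysis (τ² → ∞) has Var = ITs²/1210. At ICC 0.10 this is 132 × 145.8/1210 = 15.91 (SE 3.988). The within-cluster share of the information is 12.07/15.91 = 76%, which leaves 24% between clusters.

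| ICC | SE, random cluster effect | SE, within-cluster only | Between-cluster share |
|---|---|---|---|
| 0.05 | 3.436 | 4.097 | 30% |
| 0.10 | 3.474 | 3.988 | 24% |
| 0.20 | 3.432 | 3.760 | 17% |
| 0.30 | 3.301 | 3.517 | 12% |

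**Step 3: add the stratum.** A balanced cluster-level term replaces τ² by (1 − R²)τ². At ICC 0.10 and R² = 0.50, τ² = 16.2. Var = 33 × 145.8 × 210.6 / (484 × 145.8 + 1210 × 16.2) = 1,013,281 / 90,169 = 11.24, so SE = 3.352 and power = 84.7%.

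| ICC | SE without term | SE, R² 0.10 | SE, R² 0.25 | SE, R² 0.50 |
|---|---|---|---|---|
| 0.05 | 3.436 | 3.420 | 3.396 | 3.350 |
| 0.10 | 3.474 | 3.454 | 3.420 | 3.352 |
| 0.20 | 3.432 | 3.412 | 3.377 | 3.298 |
| 0.30 | 3.301 | 3.284 | 3.254 | 3.183 |

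The reductions are about 0.5%, 1-2% and 2.5-4%. Power at ICC 0.10 goes from 82.1% to 82.5%, 83.3% and 84.7%. At R² = 0 the variance ratio is 1.00, so the term neither gains nor costs anything in this calculation.

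**The case against.** The strongest reply is that this is an optional refinement rather than an error, and most of its parts stand.

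- **Most information is within clusters.** This is true: 70% at ICC 0.05, rising to 88% at 0.30. A reader might infer that, with two patients per cell, the design leans mainly on between-cluster comparisons. Step 2 shows that it does not.
- **The factor is not shown to be prognostic.** This also stands. The protocol's reason for balancing is logistical. A reader might suppose that past recruitment predicts acceptance of main-study entry. That is plausible, but no section says so, and past recruitment also depends on centre size.
- **Nothing is invalidated.** This stands as well. A wider standard error is conservative, the stated power holds without the term, and a within-cluster comparison is unaffected by a factor that is constant within the cluster. Minimising on one binary factor should leave little imbalance.
- **Logistic models.** A reader might carry the precision gain over to acceptance. That does not follow, because adding a covariate changes the conditional odds ratio and need not shrink its standard error.
- **A separate analysis plan may add the term.** It may. But Appendix A5 has its own statistical analysis plan section that lists the model terms, so comment on that list is fair. The possibility only means that the final analysis need not follow the list.

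What survives is that the allocation uses a factor that the listed models leave out, and that the random cluster effect does not fully stand in for it.

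**Conclusion.** The point holds as a minor one. The three models listed in Appendix A5 omit the factor on which clusters are minimised. For the primary linear model the cost is between nothing and about 4% of the standard error over ICC 0.05 to 0.30, or at most 2.6 percentage points of power at ICC 0.10 (82.1% to 84.7%). This rests on an assumed explained share of 0 to 50% and on balance of the stratum over the sequences. The documents support neither a claim of bias nor one of inadequate power for 33 clusters, and no gain in standard error is claimed for the logistic models. For those, the case is agreement with the allocation and adjustment for any imbalance that remains.

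**What to change.** In Appendix A5, Statistical Analysis Plan, add recruitment stratum (high versus low) as a fixed effect to the linear mixed model for the Decisional Conflict Scale score and to both logistic mixed models, or state why it is left out. The cost is one parameter per model. The stratum is already recorded for every cluster because the minimisation needs it, and neither the sample size nor the stated power has to change.
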